## 7. Initial Feasibility Analysis

Action report links:

- [For Liraglutide vs 2nd generation SUs](#)

Optum: <https://bwh-dope.aetion.com/#/projects/details/632/results/30594/result/0>

Marketscan: <https://bwh-dope.aetion.com/#/projects/details/633/results/30595/result/0>

Medicare: <https://bwh-dope.aetion.com/#/projects/details/634/results/30593/result/0>

- [For Liraglutide vs DPP4i](#)

Optum: <https://bwh-dope.aetion.com/#/projects/details/632/results/30606/result/0>

Marketscan: <https://bwh-dope.aetion.com/#/projects/details/633/results/30607/result/0>

Medicare: <https://bwh-dope.aetion.com/#/projects/details/634/results/30605/result/0>

Date conducted: rerun on Jan 27, 2019

Complete Aetion feasibility analysis using age, sex, and CCI as the only covariates and the primary endpoint (Section 6.3.1) as the outcome. No measures of association will be computed nor will incidence rates stratified by treatment group.

- Report patient characteristics by treatment group
- Report summary parameters of the overall study population
- Report median follow-up time by treatment group
- Report reasons for censoring in the overall study population

## 8. Initial Power Assessment

### Aetion report name:

- For Liraglutide vs 2nd SUs

Optum: <https://bwh-dope.aetion.com/#/projects/details/632/results/30597/result/1>

Marketscan: <https://bwh-dope.aetion.com/#/projects/details/633/results/30596/result/1>

Medicare: <https://bwh-dope.aetion.com/#/projects/details/634/results/30598/result/1>

- For Liraglutide vs DPP4i

Optum: <https://bwh-dope.aetion.com/#/projects/details/632/results/30608/result/1>

Marketscan: <https://bwh-dope.aetion.com/#/projects/details/633/results/30609/result/1>

Medicare: <https://bwh-dope.aetion.com/#/projects/details/634/results/30610/result/1>

Date conducted: rerun on Jan 27, 2019

In order to complete the initial power analysis, the dummy outcome of a 90-day gap in database enrollment will be used. This outcome is used to ensure that no information on the comparative risks of the outcomes of interest are available at this stage. Complete a 1:1 PS-matched comparative analysis using this outcome. PS should include only 3 covariates: age, sex, and combined comorbidity index. Power calculations are based on the formulas from Chow et al. (2008).

- Stop analyses until feasibility and power are reviewed by primary investigators and FDA. Reviewers evaluate the results of the analyses described above in Sections 7 and 8, including numbers of patients, patient characteristics, follow-up time, and reasons for censoring by treatment group, as well as overall rates of outcomes and study power. These parameters are re-evaluated and reported in the subsequent sections, after incorporating feedback and refining the protocol.

Reviewed by PI:	[name]	Date reviewed:	10/26/18
Reviewed by FDA:	[name]	Date reviewed:	1/10/19
Reasons for stopping analysis (if required):			

## 9. Balance Assessment after PS matching

Action report name:

- For Liraglutide vs 2nd Gen. SUs

Optum: <https://bwh-dope.aetion.com/projects/details/632/results/44783/result/0>

Marketscan: <https://bwh-dope.aetion.com/projects/details/633/results/45436/result/0>

Medicare: <https://bwh-dope.aetion.com/projects/details/634/results/45432/result/0>

- For Liraglutide vs DPP4i

Optum: <https://bwh-dope.aetion.com/projects/details/632/results/44786/result/0>

Marketscan: <https://bwh-dope.aetion.com/projects/details/633/results/44787/result/0>

Medicare: <https://bwh-dope.aetion.com/projects/details/634/results/45433/result/0>

Date conducted: 11/18/2019 (Medicare 11/30/2019)

After review of initial feasibility and power analyses, complete creation of the remaining covariates (see Table 1 below for list of covariates). Again, using the dummy outcome of a 90-day gap in database enrollment, complete a 1:1 PS-matched analysis. The PS should include the complete list of covariates (excluding laboratory values, which are missing in some patients).

- Provide plot of PS distributions stratified by treatment group.

Note- Please refer to **Appendix B**.

- Report covariate balance after matching.

Note- For Table 1, please refer to **Appendix B**.

- Report reasons for censoring by treatment group.

- For Liraglutide vs DPP4i

	Overall	Referent	Exposure
Dummy Outcome	0 (0.00%)	0 (0.00%)	0 (0.00%)
Death	1,271 (0.75%)	827 (0.98%)	444 (0.53%)
Start of an additional exposure	4,700 (2.79%)	1,913 (2.27%)	2,787 (3.30%)

End of index exposure	99,981 (59.27%)	45,078 (53.44%)	54,903 (65.09%)
Specified date reached	29,951 (17.76%)	16,708 (19.81%)	13,243 (15.70%)
End of patient enrollment	22,798 (13.51%)	12,483 (14.80%)	10,315 (12.23%)
Switch to other SUs (for censoring) + nursing home admission	9,989 (5.92%)	7,336 (8.70%)	2,653 (3.15%)

- For Liraglutide vs 2nd Gen. SUs

	Overall	Referent	Exposure
Dummy Outcome	0 (0.00%)	0 (0.00%)	0 (0.00%)
Death	858 (0.79%)	595 (1.10%)	263 (0.49%)
Start of an additional exposure	4,294 (3.96%)	967 (1.78%)	3,327 (6.14%)
End of index exposure	61,038 (56.33%)	27,098 (50.01%)	33,940 (62.64%)
Specified date reached	21,830 (20.15%)	13,222 (24.40%)	8,608 (15.89%)
End of patient enrollment	14,181 (13.09%)	7,902 (14.58%)	6,279 (11.59%)
Switch to other SUs (for censoring) + nursing home admission	6,163 (5.69%)	4,398 (8.12%)	1,765 (3.26%)

- Report follow-up time by treatment group.

- For Liraglutide vs DPP4i

Patient Group	Median Follow-Up Time (Days) [IQR]		
	Optum	MarketScan	Medicare
Overall Patient Population	157 [88-334]	185 [91-413]	179 [92-381]
Referent	173 [88-368]	209 [112-437]	209 [112-437]
Exposure	148 [88-302]	159 [88-331]	159 [88-331]

- For Liraglutide vs 2nd Gen. SUs

Patient Group	Median Follow-Up Time (Days) [IQR]		
	Optum	MarketScan	Medicare
Overall Patient Population	154 [88-339]	168 [88-379]	179 [98-397]
Referent	181 [100-407]	231 [128-500]	231 [128-500]
Exposure	148 [88-279]	148 [88-307]	148 [88-307]

- Report risk per 1,000 patients
  - For Liraglutide vs DPP4i

	Optum	Marketscan	Medicare
Risk per 1,000 patients	14.30	12.11	38.60

- For Liraglutide vs 2nd Gen. SUs

	Optum	Marketscan	Medicare
Risk per 1,000 patients	18.97	22.54	48.79

Action report name:

- For Liraglutide vs 2nd Gen. SUs

Optum: <https://bwh-dope.aetion.com/#/projects/details/632/results/34412/result/0>

Marketscan: <https://bwh-dope.aetion.com/#/projects/details/633/results/34413/result/0>

Medicare: <https://bwh-dope.aetion.com/#/projects/details/634/results/34414/result/0>

- For Liraglutide vs DPP4i

Optum: <https://bwh-dope.aetion.com/#/projects/details/632/results/34415/result/0>

Marketscan: <https://bwh-dope.aetion.com/#/projects/details/633/results/34416/result/0>

Medicare: <https://bwh-dope.aetion.com/#/projects/details/634/results/34417/result/0>

Date conducted: 04/25/2019

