### **13.1 For primary analysis:**

- In the PS-matched cohort from Section 9, calculate the HR for each outcome for liraglutide versus 2nd generation SU patients using a Cox proportional hazards model.

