### **13.2 For secondary analyses:**

- In the PS-matched cohort from Section 9, calculate the HR for each outcome for liraglutide versus DPP4i patients using a Cox proportional hazards model.
- In both pre-matched cohorts, perform asymmetrical trimming to remove patients with PS values below the 2.5th percentile of treated patients and above the 97.5th percentile of untreated patients. In the trimmed cohort, calculate the HR for canagliflozin versus referent patients using a Cox proportional hazards model, adjusting for deciles of the PS.

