75.6 REPAIR OF OTHER CURRENT OBSTETRIC LACERATION

75.7 MANUAL EXPLORATION OF UTERINE CAVITY, POSTPARTUM

75.9 OTHER OBSTETRIC OPERATIONS

## Appendix B: Liraglutide vs DPP4i

Optum

MarketScan

Medicare

BEFORE PS MATCHING

[figure not shown]

Figure 49: Pre-matching propensity score overlap

The c-statistics for the propensity score model, pre-matching was 0.763. The post-matching c-statistic was 0.528.

[figure not shown]

Figure 49: Pre-matching propensity score overlap

The c-statistics for the propensity score model, pre-matching was 0.749. The post-matching c-statistic was 0.523.

[figure not shown]

Figure 25: Pre-matching propensity score overlap

The c-statistics for the propensity score model, pre-matching was 0.788. The post-matching c-statistic was 0.52.

AFTER PS MATCHING

[figure not shown]

Figure 50: Post-matching propensity score overlap

[figure not shown]

Figure 50: Post-matching propensity score overlap

[figure not shown]

Figure 26: Post-matching propensity score overlap

Table 1: Liraglutide vs DPP4i

Variable	Unmatched											
	Optum			MarketScan			Medicare			POOLED		
	Reference-DPP4i	Exposure-Liraglutide	St. Diff.	Reference-DPP4i	Exposure-Liraglutide	St. Diff.	Reference-DPP4i	Exposure-Liraglutide	St. Diff.	Reference-DPP4i	Exposure-Liraglutide	St. Diff.
Number of patients	137,649	19,460		143,337	21,041		454,700	44,778		735,686	85,279	
Age												
...mean (sd)	70.07 (8.03)	66.00 (6.84)	0.55	66.74 (8.79)	63.07 (6.32)	0.48	74.48 (7.29)	70.59 (5.00)	0.62	72.15 (7.74)	67.69 (5.80)	0.65
...median (IQR)	69.00 [65.00, 76.00]	66.00 [61.00, 70.00]	0.40	64.00 [61.00, 72.00]	62.00 [60.00, 66.00]	0.26	73.00 [69.00, 79.00]	70.00 [67.00, 73.00]	0.64	70.50 (7.74)	66.59 (5.80)	0.57
Age categories												
...18-54; n (%)	3,645 (2.6%)	1,088 (5.6%)	-0.15	7,490 (5.2%)	1,773 (8.4%)	-0.13	0 (0.0%)	0 (0.0%)	#DIV/0!	11,135 (1.5%)	2,861 (3.4%)	-0.12
...55-64; n (%)	30,092 (21.9%)	6,913 (35.5%)	-0.30	68,184 (47.6%)	12,865 (61.1%)	-0.27	7,142 (1.6%)	1,114 (2.5%)	-0.06	105,418 (14.3%)	20,892 (24.5%)	-0.26
...65-74; n (%)	64,422 (46.8%)	9,363 (48.1%)	-0.03	39,328 (27.4%)	5,193 (24.7%)	0.06	250,319 (51.5%)	34,945 (78.0%)	-0.50	354,069 (48.1%)	49,501 (58.0%)	-0.20
...>=75; n (%)	39,490 (28.7%)	2,096 (10.8%)	0.46	28,335 (19.8%)	1,210 (5.8%)	0.43	197,239 (43.4%)	8,719 (19.5%)	0.53	265,064 (36.0%)	12,025 (14.1%)	0.52
Gender - United												

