Use of anticonvulsants; n (%)	4,060 (21.2%)	3,973 (20.7%)	3,106 (14.9%)	3,129 (15.1%)	8,847 (19.9%)	8,786 (19.8%)	16,013 (19.0%)	15,888 (18.8%)	0.01
Use of lithium- United; n (%)	24 (0.1%)	22 (0.1%)	37 (0.2%)	27 (0.1%)	66 (0.1%)	55 (0.1%)	127 (0.2%)	104 (0.1%)	0.03
Use of Benzo- United; n (%)	2,251 (11.7%)	2,238 (11.7%)	2,514 (12.1%)	2,553 (12.3%)	4,924 (11.1%)	4,945 (11.1%)	9,689 (11.5%)	9,736 (11.5%)	0.00
Use of anxiolytics/hypnotics- United; n (%)	1,429 (7.4%)	1,386 (7.2%)	1,747 (8.4%)	1,702 (8.2%)	3,365 (7.6%)	3,365 (7.6%)	6,541 (7.8%)	6,453 (7.7%)	0.00
Use of dementia meds- United; n (%)	186 (1.0%)	205 (1.1%)	153 (0.7%)	146 (0.7%)	895 (2.0%)	917 (2.1%)	1,234 (1.5%)	1,268 (1.5%)	0.00
Use of antiparkinsonian meds- United; n (%)	664 (3.5%)	666 (3.5%)	630 (3.0%)	638 (3.1%)	1,810 (4.1%)	1,794 (4.0%)	3,104 (3.7%)	3,098 (3.7%)	0.00
Any use of pramipartide; n (%)	2 (0.0%)	5 (0.0%)	8 (0.0%)	25 (0.1%)	**	**	**	**	**
Any use of 1st generation sulfonylureas; n (%)	4 (0.0%)	0 (0.0%)	1 (0.0%)	1 (0.0%)	**	**	**	**	**
Entresto (sacubitril/valsartan); n (%)	50 (0.3%)	47 (0.2%)	18 (0.1%)	13 (0.1%)	44 (0.1%)	27 (0.1%)	112 (0.1%)	887 (0.1%)	0.00
Initiation as monotherapy ; n (%)	1,829 (9.5%)	0 (0.0%)	1,585 (7.6%)	0 (0.0%)	3,010 (6.8%)	0 (0.0%)	6,424 (7.6%)	#VALUE!	#VALUE!
Labs							39.964	39.964	
Lab values- HbA1c (%); n (%)	7,630 (39.8%)	7,216 (37.6%)	1,331 (6.4%)	1,167 (5.6%)	N/A	N/A	8,961 (22.4%)	8,383 (21.0%)	0.03
Lab values- HbA1c (%)(within 3 months); n (%)	6,032 (31.4%)	5,538 (28.9%)	1,052 (5.1%)	916 (4.4%)	N/A	N/A	7,084 (17.7%)	6,454 (16.1%)	0.04
Lab values- HbA1c (%)(within 6 months); n (%)	7,630 (39.8%)	7,216 (37.6%)	1,331 (6.4%)	1,167 (5.6%)	N/A	N/A	8,961 (22.4%)	8,383 (21.0%)	0.03
Lab values- BNP; n (%)	211 (1.1%)	206 (1.1%)	25 (0.1%)	34 (0.2%)	N/A	N/A	236 (0.6%)	240 (0.6%)	0.00
Lab values- BNP (within 3 months); n (%)	117 (0.6%)	121 (0.6%)	14 (0.1%)	28 (0.1%)	N/A	N/A	131 (0.3%)	149 (0.4%)	-0.02
Lab values- BNP (within 6 months); n (%)	211 (1.1%)	206 (1.1%)	25 (0.1%)	34 (0.2%)	N/A	N/A	236 (0.6%)	240 (0.6%)	0.00
Lab values- BUN (mg/dl); n (%)	7,901 (41.2%)	7,376 (38.4%)	1,341 (6.5%)	1,179 (5.7%)	N/A	N/A	9,242 (23.1%)	8,555 (21.4%)	0.04
Lab values- BUN (mg/dl)(within 3 months); n (%)	6,155 (32.1%)	5,577 (29.1%)	1,038 (5.0%)	901 (4.3%)	N/A	N/A	7,193 (18.0%)	6,478 (16.2%)	0.05
Lab values- BUN (mg/dl)(within 6 months); n (%)	7,901 (41.2%)	7,376 (38.4%)	1,341 (6.5%)	1,179 (5.7%)	N/A	N/A	9,242 (23.1%)	8,555 (21.4%)	0.04

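### The matched tables show that some listed covariates were not working terms in the propensity score, and small same-direction differences in insulin use and endocrinologist care remain in the matched Cox analyses

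*Combined protocol and SAP*

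**What the plan says.** Section 9 asks the team to "complete creation of the remaining covariates (see Table 1 below for list of covariates"), and then sets the content of the propensity score (PS): "The PS should include the complete list of covariates (excluding laboratory values, which are missing in some patients"). The list is Table 1 in Appendix B, so every non-laboratory row is meant to be in the score. The plan sets no balance limit.

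For the outcome analysis, Section 13.1 gives the sulfonylurea (SU) comparison as an HR for liraglutide versus 2nd "generation SU patients using a Cox proportional hazards model". Section 13.2 says to "calculate the HR for each outcome for liraglutide versus DPP4i patients using a Cox proportional hazards model". Neither names a covariate. Section 13.2 also plans a model in the trimmed cohorts, "using a Cox proportional hazards model, adjusting for deciles of the PS".

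Sections 5.1 and 6.1 make DPP4i the primary comparator, while Section 13.1 attaches the primary label to SU. That conflict is a separate matter; DPP4i is treated as primary here.

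**The concern.** When a covariate enters a well-fitted PS, 1:1 matching on tens of thousands of pairs should balance it closely, whatever the starting gap. Obesity does this: the pooled DPP4i standardised difference goes from -0.32 to 0.00. Some other listed rows do not. One has no exposed patients at all, and another is further apart after matching than before. Those rows point to a PS that is not the one Section 9 describes.

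The Section 10 stop point asks reviewers to judge balance from this table. They can do so only if they know which terms were fitted and if no error cell covers a large difference. The remaining differences in insulin and endocrinologist care have the same sign in every database, so pooling will not average them out, and the matched Cox models have no covariate term to absorb them.

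**Working it through.** **Formula and the plan's own figures.** Standardised difference = (p_ref - p_exp) / sqrt{[p_ref(1 - p_ref) + p_exp(1 - p_exp)]/2}. Pooled matched counts from Appendix B:

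| Row | Referent | Liraglutide | Pairs | From counts | Printed |
|---|---|---|---|---|---|
| Insulin, DPP4i | 14,554 | 15,311 | 84,345 | -0.024 | -0.02 |
| Insulin, SU | 11,317 | 11,915 | 54,182 | -0.027 | -0.03 |
| Endocrinologist visit, DPP4i | 17,685 | 19,269 | 84,345 | -0.045 | -0.04 |
| Endocrinologist visit, SU | 11,190 | 12,528 | 54,182 | -0.060 | -0.06 |

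The printed values reproduce. The -0.04 comes from the rounded percentages 21.0 and 22.8.

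**Monotherapy, DPP4i matched.** Order: Optum, MarketScan, Medicare.

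- Referents 1,829/19,187, 1,585/20,777 and 3,010/44,381; liraglutide 0 in each. Standardised differences are 0.459, 0.406 and 0.381. Pooled, 6,424 versus 0 gives 0.406. The table prints #VALUE! for the pooled liraglutide cell and the pooled difference.
- In a maximum-likelihood logistic PS, the fitted scores of patients with a given indicator sum to the number exposed among them. With none exposed, every such score goes to about 0, and those referents should hardly ever be matched.
- In fact 1,829/15,454 = 11.8%, 1,585/15,217 = 10.4% and 3,010/42,437 = 7.1% of them were matched. For all referents the shares are 19,187/137,649 = 13.9%, 20,777/143,337 = 14.5% and 44,381/454,700 = 9.8%.
- If those referents ranked lowest, the post-match c-statistic would be at least 0.5 + p_ref/2 = 0.548, 0.538 and 0.534. For Optum, Appendix B reports: "The post-matching c-statistic was 0.528". The others are 0.523 and 0.52.

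The row as tabulated was therefore not a working term. "Any use of 1st generation sulfonylureas; n" points the same way in Optum on tiny counts (26 vs 0 before matching, 4 vs 0 after).

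The zero is doubtful. In the unmatched Optum SU table 1,801/12,485 = 14.4% of liraglutide users start as monotherapy, and the unmatched Optum DPP4i table has 2,950 treatment-naive liraglutide initiators.

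**Hyperthyroidism and dipstick urinalysis, DPP4i, standardised difference before → after matching.**

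| Row | Optum | MarketScan | Medicare | Pooled z after |
|---|---|---|---|---|
| Hyperthyroidism | 0.016 → 0.038 | 0.007 → 0.032 | 0.015 → 0.024 | 5.9 (871 vs 641) |
| Dipstick | 0.051 → 0.034 | -0.006 → 0.053 | 0.061 → 0.031 | 7.5 (32,920 vs 31,417) |

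All six post-match database differences exceed chance (z from 3.3 to 5.4). Hyperthyroidism widens in each database. Dipstick widens in MarketScan and only partly narrows in the other two.

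**Insulin and endocrinologist visit by database, matched.** Insulin: -0.029, -0.026, -0.020 (DPP4i) and -0.018, -0.046, -0.022 (SU). Endocrinologist visit: -0.051, -0.048, -0.042 and -0.056, -0.074, -0.055. All twelve have the same sign. Optum SU insulin (2,389 vs 2,476) is within chance, z = -1.4, p = 0.16.

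**Effect on the HR.** The associations are assumptions; the documents give none. Shift = exp(Δ × ln HR) - 1, where Δ is liraglutide minus referent prevalence. For age, the log-HR shift is b × Δmean + (b²/2) × Δvariance, weighted over databases by the expected events in Section 10.

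| Source (assumed HR) | DPP4i | SU |
|---|---|---|
| Insulin (1.3 to 2.0) | Δ 0.0090: +0.2 to +0.6% | Δ 0.0110: +0.3 to +0.8% |
| Endocrinologist (0.8 to 1.25) | Δ 0.0188: ±0.4% | Δ 0.0247: ±0.6% |
| Age (b = 0.05 to 0.10 per year) | +0.1 to -0.7% | +0.6 to +0.4% |

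The net is within about 1% for DPP4i and about 0.2 to 2% for SU. The target log HR is ln 0.87 = -0.139, and the SE at 3,262 events is 2/√3,262 = 0.035. The SU upper end is thus about 14% of the target effect and about half an SE.

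**Power if every monotherapy pair were lost.** 84,345 - 6,424 = 77,921 pairs; 2 × 77,921 × 21.67/1,000 = 3,377 events. Power = Φ(0.139 × √events/2 - 1.96). At 3,655.5 events this reproduces the stated 0.988; at 3,377 it gives 0.982.

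**The case against.** Several points on the other side stand.

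- Large z-scores partly reflect sample size. The endocrinologist z of 9.3 (DPP4i) is a standardised difference of only 0.045. Matching removed most of the original gaps: pooled insulin was 0.36 (DPP4i) and 0.46 (SU) in size before matching, and endocrinologist visit 0.35 and 0.50.
- Some omissions are harmless. The total insulin row is the exact sum of its concomitant and past rows (Optum DPP4i: 1,846 + 1,257 = 3,103). Any endocrinologist visit is the union of two time windows, whose own DPP4i rows are closer (z about 3.0 and 2.5).
- A PS holding literally every non-laboratory row cannot be fitted. Liver disease and drug abuse are all zero, the insulin rows are collinear, and monotherapy as coded is perfectly separated.
- In a matched analysis the matching is the adjustment, and a Cox model with treatment alone is conventional.

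A reader might infer that the planned Cox models adjust for nothing. The documents do not support that: the trimmed-cohort model adjusts for PS deciles. It is only a partial answer, because those deciles come from the PS in question.

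A reader might also infer that insulin and endocrinologist care were left out of the score altogether. The tables do not show this; the pattern fits a score that held the component rows. Nor does the gap in age under 55 prove omission. A linear age term could produce it, and in Medicare the row is 0 versus 0.

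**Conclusion.** The point holds as a mismatch between specification and delivery, with a small expected bias. The evidence is close to conclusive for monotherapy as tabulated in the three DPP4i cohorts and strong for hyperthyroidism and dipstick urinalysis. The SU monotherapy rows (-0.048, -0.049, +0.009) give no such proof.

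It is tempting to dismiss the matter because every standardised difference lies below 0.1, a common convention that the plan does not itself adopt. That is not so. Monotherapy is about 0.41, and in the matched SU table HbA1c (0.13), total cholesterol (0.13) and glucose (0.12) also exceed it, although laboratory values are outside the score by design.

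It is equally tempting to treat 0.41 as real confounding. With 7.6% versus 0%, the bias factor 1/(1 + 0.076 × (RR - 1)) would be 1.04 at an assumed RR of 0.5 and 0.93 at an RR of 2. Because the zero is probably a coding error, the documents do not support that size. The true monotherapy balance is unknown until the variable is corrected.

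For insulin, endocrinologist care and age, the shift is within about 1% for DPP4i and up to about 2% for SU, conditional on the assumed associations. This is a cheap improvement and does not threaten the study.

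**What to change.** Before outcomes are run (the date fields in Sections 12 and 13 are blank in this version):

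1. Correct the monotherapy variable in the DPP4i tables, replace the error cells, and report its true balance.
2. List the terms actually in each database's PS. Re-fit with the omitted covariates that are estimable and not redundant: corrected monotherapy, hyperthyroidism, urinalysis and any endocrinologist visit. Enter age as a spline or with its categories. Leave out all-zero and exactly collinear rows, and amend Section 9 to say so.
3. In Sections 13.1 and 13.2, report beside the unadjusted matched HR a matched Cox model adjusted for age (spline), insulin, endocrinologist visit and corrected monotherapy.

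The third step costs one extra analysis with variables already built. A re-match costs more: matched numbers, Table 1, follow-up and censoring tables and Section 10 power all change, and the balance and power review dated 12/9/19 and 12/20/19 would have to be repeated. Power is not an obstacle, since even the worst case above leaves 0.982 for the pooled DPP4i comparison.

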## 10. Final Power Assessment

Date conducted: 12/01/2019

- Re-calculate power in the appropriate excel table, using the revised number of matched patients from the PS-match in Section 9. All other parameters in the table should be the same as in Section 8. If the study is to be implemented in more than one database, copy and paste excel sheet to report power for each database separately and for the pooled analysis that uses data

from all databases together. Power calculations are based on the formulas from Chow et al. (2008).

- For Liraglutide vs DPP4i

- Pooled

Superiority Analysis		Non-inferiority Analysis	
Number of patients matched		Number of patients matched	
Reference	84,345	Reference	84,345
Exposed	84,345	Exposed	84,345
Risk per 1,000 patients	21.67	Risk per 1,000 patients	21.67
Desired HR from RCT	0.87	Assumed HR from RCT	1
Alpha (2-sided)	0.05	Alpha (2-sided)	0.05
		Non-inferiority margin	1.3
Number of events expected	3655.5123	Number of events expected	3655.5123
Power	0.987775093	Power	0.999999999

- Optum

Superiority Analysis		Non-inferiority Analysis	
Number of patients matched		Number of patients matched	
Reference	19,187	Reference	19,187
Exposed	19,187	Exposed	19,187
Risk per 1,000 patients	14.30	Risk per 1,000 patients	14.30
Desired HR from RCT	0.87	Assumed HR from RCT	1
Alpha (2-sided)	0.05	Alpha (2-sided)	0.05
		Non-inferiority margin	1.3
Number of events expected	548.7482	Number of events expected	548.7482
Power	0.371306397	Power	0.867151513

▪ Marketscan

Superiority Analysis		Non-inferiority Analysis	
Number of patients matched		Number of patients matched	
Reference	20,777	Reference	20,777
Exposed	20,777	Exposed	20,777
Risk per 1,000 patients	12.11	Risk per 1,000 patients	12.11
Desired HR from RCT	0.87	Assumed HR from RCT	1
Alpha (2-sided)	0.05	Alpha (2-sided)	0.05
		Non-inferiority margin	1.3
Number of events expected	503.21894	Number of events expected	503.21894
Power	0.345542948	Power	0.837143294

▪ Medicare

Superiority Analysis		Non-inferiority Analysis	
Number of patients matched		Number of patients matched	
Reference	44,381	Reference	44,381
Exposed	44,381	Exposed	44,381
Risk per 1,000 patients	38.60	Risk per 1,000 patients	38.60
Desired HR from RCT	0.87	Assumed HR from RCT	1
Alpha (2-sided)	0.05	Alpha (2-sided)	0.05
		Non-inferiority margin	1.3
Number of events expected	3426.2132	Number of events expected	3426.2132
Power	0.982819492	Power	0.999999995

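### Section 10 expected events and power are not shown to describe the final matched cohort, and the two pooled risks are unweighted means that do not agree with the database tables

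*Combined protocol and SAP*

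**What the plan says.** Section 9 dates the full-covariate match 18 November 2019 (Medicare 30 November 2019) and describes it thus: "Again, using the dummy outcome of a 90-day gap in database enrollment, complete a 1:1 PS-matched analysis". Later in Section 9 come the risks per 1,000 patients: 14.30, 12.11 and 38.60 against DPP4i, and 18.97, 22.54 and 48.79 against sulfonylureas (SU), for Optum, MarketScan and Medicare in that order. Directly below them stands a second set of report links, with much lower result numbers (34412-34417, against 44783-45436 for the November runs) and the line "Date conducted: 04/25/2019".

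Section 10 ("Date conducted: 12/01/2019") recalculates power "using the revised number of matched patients from the PS-match in Section 9" and adds: "All other parameters in the table should be the same as in Section 8". Section 8 carries the line "Date conducted: rerun on Jan 27, 2019". It also says that patient numbers, overall outcome rates and power are looked at again in later sections. Section 10 gives those same items to the principal investigators, FDA and advisory board for the decision to proceed.

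**The concern.** Expected events are N times risk, so both factors should describe the same patients. Here N is from November 2019. The risk appears to be from April 2019, and by date it belongs neither to the Section 8 run nor to the final match. The November run, as described, cannot supply a 3P-MACE risk.

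Which cohort the risk describes matters, because matching changes the population. In the DPP4i comparison (Appendix B, arms combined), mean age goes from 71.7 before matching to 67.7 after, any prior hospitalisation from 13.4% to 8.6%, and heart failure from 12.6% to 10.1%. A risk from the unmatched population would probably be too high for the matched one. The single-database non-inferiority figures, which lie between 0.81 and 0.90 in the two commercial databases, are the ones whose reading could change.

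The pooled tables raise a separate question: whether their events agree with those of the three databases that they pool.

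**Working it through.** **Formulas.** Events D = 2 × N per arm × risk / 1000. Power = Φ(|ln HR| × √(D/4) − 1.96), with HR 0.87 for superiority and 1.3 (margin, true HR 1) for non-inferiority (NI), two-sided alpha 0.05.

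**Reproducing the plan.** All eight tables reproduce: events exactly, power within 0.0003. Examples:
- DPP4i, Optum: 2 × 19,187 × 14.30/1000 = 548.7; NI power 0.867.
- DPP4i, MarketScan: 2 × 20,777 × 12.11/1000 = 503.2; NI power 0.837.
- SU, MarketScan: 2 × 13,591 × 22.54/1000 = 612.7; NI power 0.901.

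This confirms that Section 10 is the November N times the Section 9 risks.

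**Population shift, DPP4i comparison.**
- Age before matching: (735,686 × 72.15 + 85,279 × 67.69)/820,965 = 71.7. After: 67.62 and 67.74 by arm, so 67.7.
- Hospitalisation: (102,375 + 7,327)/820,965 = 13.4%, against (7,322 + 7,231)/168,690 = 8.6%.
- Heart failure: (95,015 + 8,670)/820,965 = 12.6%, against (8,561 + 8,505)/168,690 = 10.1%.

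**Sensitivity.** The documents give no 3P-MACE risk for the November cohort, so no single corrected figure exists. Assume that the matched risk is 70-85% of the printed value:

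| DPP4i comparison | Events | NI power | Superiority power |
|---|---|---|---|
| Optum | 384-466 | 0.73-0.81 | |
| MarketScan | 352-428 | 0.69-0.77 | |
| Pooled, from printed 3655.5 | 2559-3107 | >0.999 | 0.94-0.97 |
| Pooled, from N-weighted 4478.2 | 3135-3806 | >0.999 | 0.97-0.99 |

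Pooled 90% power needs 2168 events for superiority, which is 41% (DPP4i) or 34% (SU) below the printed pooled events. For non-inferiority it needs 611, more than 80% below.

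**The 22.54.** SU-to-DPP4i risk ratios: MarketScan 22.54/12.11 = 1.86; Optum 18.97/14.30 = 1.33; Medicare 48.79/38.60 = 1.26. The two matched MarketScan cohorts look alike (mean age about 63, ischemic heart disease 31-33%). NI power of 90% needs about 610.6 events and the table has 612.7, so a risk 0.3% lower (1 − 610.6/612.7) reaches that line. In the same part of Section 9, the by-arm follow-up medians and IQRs printed for MarketScan and Medicare are identical in both comparisons, which is another reason to check this block against its source.

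**Pooled risk.**
- DPP4i: (14.30 + 12.11 + 38.60)/3 = 21.67, the printed value. Database events sum to 548.7 + 503.2 + 3426.2 = 4478.2, not 3655.5. Weighted risk = 4478.2/(2 × 84,345) × 1000 = 26.55. Superiority power is 0.997, not 0.988.
- SU: (18.97 + 22.54 + 48.79)/3 = 30.10, the printed value. Database events sum to 464.9 + 612.7 + 2765.2 = 3842.8, not 3261.8. Weighted risk = 3842.8/(2 × 54,182) × 1000 = 35.46. Superiority power is 0.991, not 0.978.

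**The case against.** **Carrying the risk forward is the written rule.** True: Section 10 tells the analyst to change only N. But the rule points to Section 8, run in January 2019, and the listed report is from April, so the rule does not identify the source either.

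**The link to April rests on layout.** This stands. In Sections 7, 8, 9 and 13 the report block comes before its content; here it follows the risk table, and it could be left over from a previous round of work. It is the natural reading, not a stated fact.

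**Nothing says that the risks are unmatched.** This also stands. They are printed in the section on balance after matching. A reader might infer an unmatched source from Section 7 ("Report summary parameters of the overall study population"). That is a different run, the line does not mention event rates, and there *overall* contrasts with reporting by treatment group. The last dated definition change (22 April 2019) precedes the April report, and an earlier date alone does not show a different risk.

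**The 22.54 may be genuine.** Matched MarketScan SU patients have more ischemic heart disease than Optum (31.5% against 29.5%) and longer median follow-up (168 against 154 days). But the same holds in the DPP4i comparison (32.6% against 29.8%; 185 against 157 days), where the MarketScan risk is the lower one. An unmatched source would not explain it either, since the unmatched MarketScan cohorts are also alike. That justifies checking the figure, not replacing it.

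**No decision turns on it.** Largely right. The 90% in Section 1.4 is for the primary endpoint, no per-database threshold is stated, and Optum and MarketScan against DPP4i are already printed below 0.90.

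**Conclusion.** Two things hold. First, the source of the Section 10 risks is undocumented, so the printed events and power are not shown to describe the matched cohort. Second, and on the documents alone, the pooled risks are wrong as written: simple averaging gives pooled events 18% (DPP4i) and 15% (SU) below the sum of the plan's own database tables.

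A reader might go further and conclude that the tables describe the wrong patients or that power is overstated. The documents do not support that. The direction of any error in the database risks is unknown, and the 70-85% factor is an assumption that applies only if the risks are unmatched. In the pooled tables the averaging error works the other way: database risks would have to fall by 18% (DPP4i) or 15% (SU) before correctly weighted events dropped below the printed totals. A reader might also apply the other databases' ratios to MarketScan SU (1.26-1.33 × 12.11, about 15.3-16.1 per 1,000; 415-438 events; NI power 0.76-0.78). Nothing in the documents justifies that transfer; it shows only why 22.54 deserves a check.

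Pooled non-inferiority power stays above 0.999 throughout. What could change is how the single-database figures are read. This is a minor point.

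**What to change.** 1. State in Section 9 which run and which cohort, matched or not, supplied each risk.
2. Read the overall 3P-MACE risk, both arms combined, from the final matched cohort in each database. Otherwise, label the risk as carried forward and show power over a stated range.
3. Verify 22.54 against its source report, together with the repeated follow-up rows beside it.
4. Re-issue the Section 10 tables with the pooled risk weighted by matched N. On the present database risks that gives 26.55 and 35.46 per 1,000.

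The cost is one count per database and a revised set of tables. A count over both arms together gives no comparative information, so it keeps the protection for which the dummy outcome was chosen. Some single-database power figures may become less favourable; the pooled superiority figures rise slightly on the present risks.
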